2. INTRODUCTION

Etrasimod is an orally administered, selective, synthetic S1P_{1,4,5} modulator that is being developed to treat immune-mediated inflammatory disorders, including UC, AA, AD, and EoE. The S1P₁ is a cell surface expressed protein that has been shown to regulate lymphocyte migration out of lymphoid tissues. Synthetic small molecule S1P₁ agonists have been observed to act as functional antagonists by inducing sustained receptor internalization, thus inhibiting lymphocyte migration out of lymphoid tissues and lowering the amount of peripheral blood lymphocytes available to be recruited to sites of inflammation. Modulation of the S1P/S1P receptor axis is thought to be a potential therapeutic approach to the management of immune-mediated inflammatory disorders.

2.1. Study Rationale

This sub study is being conducted to assess the feasibility of conducting a Phase 1 etrasimod study as a hybrid decentralized clinical trial with dosing by study personnel at the CRU and remote collection of PK, safety and tolerability data. The specific objectives of the sub study are to determine the PK and to assess the safety and tolerability of etrasimod clinical IR tablets 2 mg under fasted conditions in healthy adult participants in a hybrid DCT design.

This study is being conducted under the main study C5041034 as a sub study for the following reasons. The assessments and the objectives of this study are distinctly different from the main study; however, the analysis plan of the sub study includes comparison of the results of the sub study conducted as a hybrid DCT design with corresponding results of the main study conducted at the CRU.

2.2. Background

The pharmacology, safety pharmacology, PK, metabolism, toxicology and clinical dose-ranging efficacy and safety of etrasimod oral administration had been comprehensively studied. A summary of relevant, currently available data is provided in this protocol. Additional details and further information for this compound could be found in the current IB.

The sub study is being conducted to assess the feasibility of conducting a Phase 1 etrasimod study as a hybrid decentralized clinical trial ^{1,2} with dosing by study personnel at the CRU and remote collection of PK, safety and tolerability data. DCTs have the potential to expand access to more diverse patient populations and improve trial efficiencies.³ Advances in clinical care using electronic communications and information technology to interact with trial participants in different locations (ie, telehealth) allow for fewer in-person visits to clinical trial sites. DHTs, for example, have expanded the types of trial-related data that can be obtained remotely from trial participants. By enabling remote participation, DCTs may enhance convenience for trial participants, reduce the burden on caregivers, and facilitate research on rare diseases and diseases affecting populations with limited mobility or access to traditional trial sites. This may help improve trial participant engagement, recruitment, enrollment, and retention of a meaningfully diverse clinical population.

2.2.1. Nonclinical Pharmacology

A summary of the nonclinical investigational programs can be found in the current IB.

2.2.2. Nonclinical Pharmacokinetics and Metabolism

Etrasimod is eliminated primarily hepatically by extensive metabolism involving oxidation of etrasimod, along with dehydrogenation and conjugation, and showed no human specific metabolite(s) compared to those observed in the toxicology species. The main CYP enzymes involved in the oxidative metabolism of etrasimod are CYP2C8 (38%), CYP2C9 (37%), and CYP3A4 (22%), and with CYP2C19 and CYP2J2 being minor contributors (1% each). There are no major circulating metabolites and etrasimod is the primary circulating drug entity.

Additional information of the nonclinical PK and metabolism of etrasimod is available in the current IB.

2.2.3. Nonclinical Safety

Etrasimod was well tolerated across the general toxicity program conducted in CD-1 mice, Sprague Dawley rats, and beagle dogs, with no etrasimod-induced mortality following repeat administration up to 91-days, 6-months, and 9-months at 20, 150, and 15 mg/kg/day in mice, rats, and dogs, respectively. Most etrasimod-related findings were considered nonadverse, reversible upon cessation of treatment, and/or readily monitorable in the clinic. One of the most common adverse effects across species was decreased body weight and/or body weight gain, with associated decreases in food consumption. The primary target organs identified across all species were lymphoid tissues, lung, and liver. In addition, the heart was identified as a target organ in the dog. When administered at doses within and above the therapeutic range (up to 858 × in rats and 380 × in dogs over the total C_{max} exposure at the proposed human dose for the treatment of UC) in safety pharmacology studies, etrasimod showed no effect on CNS, respiratory, or cardiovascular function.

The potential effects of etrasimod on the cardiovascular system were investigated in a series of in vitro and in vivo studies. In vitro, etrasimod increased hERG currents by 31.4% at 1 mm and 58.9% at 3 mm. These concentrations are approximately 193 × and 578 × over the free C_{max} exposure at the proposed human dose for the treatment of UC. An IC50 for hERG current inhibition could not be established for etrasimod since only increases in hERG channel current, rather than inhibition, were observed. Based on the G protein receptor signaling associated with the primary PD activity, etrasimod was observed to activate GIRK currents in vitro. GIRK1 and GIRK4 are the 2 homologous subunits of I_{KACh} that interact with Gβγ to mediate the activation of the potassium channel.⁴ G-protein signaling via GIRK I_{KACh} channel activation in cardiac cells is considered to be responsible for the transient cardiovascular effects seen with first dose of S1P receptor modulators.^{5, 6, 7} At I_{KACh} in primary human atrial cardiomyocytes, etrasimod exhibited an EC50 of 29.9 nM and there was no difference between S1P and etrasimod in the time course of I_{KACh} activation. The maximal current induced by etrasimod, however, was 90% of that observed with carbachol and was 10 × lower (based on EC50) than S1P itself.

Etrasimod was not mutagenic or clastogenic in in vitro genetic toxicity studies and is not considered genotoxic in rats or to pose a genotoxic risk to humans. There were no etrasimod-related effects on spermatogenesis or fertility in males at any dose level evaluated. In the embryo-fetal development studies in rats and rabbits, administration of etrasimod during the period of organogenesis resulted in increased post implantation loss and decreased mean litter numbers and proportions of viable fetuses in both species. The embryo lethality and fetal malformations noted with etrasimod in the rat and rabbit embryo-fetal development studies are consistent with similar findings observed with approved S1P modulators^{8, 9, 10, 11} and are believed to be a result of the important role of S1P₁ in embryogenesis, including vascular and neural development.¹²

Further details of the nonclinical safety program are provided in the current IB.

2.2.4. Clinical Overview

Safety, tolerability and PK of etrasimod were evaluated in 15 Phase 1 studies in healthy adult participants. Efficacy and safety of etrasimod was evaluated in 3 completed Phase 2, 6 ongoing Phase 2, 4 completed Phase 3 and 1 ongoing Phase 3 studies across several disease indications. Clinical pharmacology data established the PK properties of etrasimod with or without food and in specified participant subpopulations (eg, participants with renal or hepatic impairment), and included comprehensive drug interaction studies to inform dosing recommendations.

A complete summary of the clinical data relevant to etrasimod and its study in human participants is provided in the current edition of the IB.

2.2.4.1. Pharmacokinetic Overview of Etrasimod

Etrasimod is absorbed with a median T_{max} of 4 hours after administration as an etrasimod 2 mg IR tablet in the fasted state, and up to 6 hours in the fed state. Food did not affect etrasimod exposure measures (C_{max} and AUC). Plasma C_{max} and AUC values of etrasimod are dose proportional following a single dose of 0.1 to 5 mg. For multiple-doses of etrasimod over a range of 0.7 to 2 mg once daily, steady-state C_{max} increased dose proportionally and steady-state AUC₀₋₂₄ increased slightly greater than dose proportionally. Apparent dose proportional increases were also observed for mean steady-state C_{max} and AUC₀₋₂₄ values from 2 to 4 mg once daily dosing in healthy participants. The time to reach approximate steady-state for etrasimod exposure measures (C_{max}, AUC₀₋₂₄, C_{trough}) is within 7 days of the first dose. Mean Rac for etrasimod exposure measures are <3-fold with once daily dosing. These observations are consistent with etrasimod's elimination (effective) half-life of approximately 30 hours. The mean oral Vz/F of etrasimod ranged from 50 to 103 L in healthy participants across evaluated single and multiple-dose levels and Phase 1 studies, indicating extravascular distribution. The mean oral plasma CL/F of etrasimod following single and multiple-dose administration of etrasimod was low and ranged from 1.13 to 1.43 L/h and 0.97 to 1.70 L/h, respectively, in healthy participants across evaluated dose levels in the Phase 1 studies.

The human mass balance study identified 2 oxidative metabolites, AR503641 (M3) and AR504344 (M6) present in systemic circulation, though minor as they are each <10% of total radioactivity. The oxidation of etrasimod occurs by 3 CYPs (CYP2C8, CYP2C9 and CYP3A4). Etrasimod is primarily eliminated in feces, with no parent drug detected in the urine.

2.2.4.2. Safety Overview of Etrasimod

As of 30 Aug 2022, a total of 2119 participants (419 healthy participants and 1700 participants with disease) have been exposed to etrasimod in clinical development programs. Clinical evidence in participants of healthy status, UC, CD, AD, AA or EoE to date have demonstrated that etrasimod is well tolerated in humans.

Across all clinical studies (Phase 1 to Phase 3), etrasimod caused expected mild, transient, and generally asymptomatic reduction in HR at first dose and very few participants with HR < 50 bpm. These reductions were greatest following first dose and lessened upon repeat dosing due to development of tolerance, allowing HR to return to baseline. The HR effects are related to S1P₁ localized on atrial myocytes that activate GIRK channels, which are transient and not clinically adverse or associated with safety findings.

Etrasimod 2 mg administered once daily demonstrated an acceptable safety profile up to 52 weeks in controlled studies and up to 104 weeks in uncontrolled studies. There was a low incidence of SDEIs such as infections, including severe (ie, Grade ≥3) infections, opportunistic infections, and herpes infections (herpes zoster and herpes simplex), cardiac safety events (bradycardia, AV conduction delays, and hypertension), malignancies, liver injury (liver transaminase elevation and bilirubin elevation), macular oedema, and pulmonary disorders (airflow obstruction and decreased gas exchange) in participants who were treated with etrasimod 2 mg.

2.3. Benefit/Risk Assessment

Etrasimod, an investigational, oral, and once daily S1P receptor modulator, is not expected to provide any clinical benefit to healthy participants. In this study, etrasimod will be administered at single doses of 2 mg. This study is being conducted primarily to generate safety, tolerability, pharmacokinetic data for the etrasimod tablets in a hybrid DCT design.

Etrasimod was determined to be well tolerated and to have an acceptable safety profile in both healthy participant and diseased clinical studies.

More detailed information about the known and expected benefits and risks and reasonably expected AEs of etrasimod may be found in the IB, which is the SRSD for this study. Refer to the Study Intervention(s) table in Section 6.1 for a complete description of SRSDs.

2.3.1. Risk Assessment

Potential Risk of Clinical Significance	Summary of Data/Rationale for Risk	Mitigation Strategy
	Study Intervention(s) Etrasimod	
S1P receptor modulator-related effects (class effect of AEs observed with S1P receptor modulators) may be observed. • cardiovascular events (eg, bradycardia, atrioventricular conduction delay and hypertension) • infections (severe infections, opportunistic infections, Herpes simples and Herpes zoster) • macular edema • pulmonary events (airflow obstruction or altered gas exchange) • liver injury • malignancy	Clinical experience with other S1P receptor modulators for the treatment of MS and UC. • The totality of etrasimod clinical studies (Phase 1, 2 and 3 studies) have shown that 2 mg etrasimod is well-tolerated with no clinically significant safety signals.	Exclusion of participants at risk. Short duration of treatment. Safety labs at screening and baseline and when deemed necessary by the investigator throughout the study. AE monitoring throughout the study.
S1P receptor modulator-specific lymphocyte level decreases.	Dose-dependent reductions in peripheral lymphocyte counts are an expected PD effect of etrasimod. The totality of clinical studies following single dose administration of study intervention is well-tolerated with a return to normal range by Day 7.	Participants with conditions or risk factors related to infection or immune function will be excluded from the study. Participants will be assessed for safety including infections at regular intervals throughout the study to identify and mitigate the potential risks.
First dose cardiac effect	S1P receptor modulators class of drugs is associated with an expected, on-target effect of reducing HR when first dosed. The totality of clinical data up to date across Phase 1 to 3 studies across several indications indicate that etrasimod 2 mg is well-tolerated with modest	Participants with elevated cardiac risk factors will be excluded from participation in the study. Specifically, Section 5.2 Exclusion Criterion #1 is aligned with IB to require "Myocardial infarction, unstable angina, stroke/transient ischemic attack, decompensated heart failure requiring

Potential Risk of Clinical Significance	Summary of Data/Rationale for Risk	Mitigation Strategy
	HR reduction that is maximal on the first day of dosing without major clinically relevant cardiac safety events.	hospitalization, or Class III/IV heart failure ≤6 months prior to study intervention."
	surety events.	Hourly HR monitoring for the first 6-hours post first dose will be conducted for all dose periods.
		Participants with cardiac effects associated with first dose will be required to permanently discontinue study intervention.
Reproductive and developmental toxicity.	The effects of etrasimod on human fertility and embryonic development are unknown.	WOCBP who are pregnant, lactating, or breastfeeding will be excluded from this study.
	Nonclinical reproductive and developmental toxicity studies of etrasimod combined with data and knowledge on the role of S1P ₁ in vascular embryogenesis demonstrate embryo fetal toxicity of etrasimod if used during pregnancy.	WOCBP will be eligible only if she and her partner(s) agree(s) with the contraceptive method as described in Section 10.4.4 throughout the study period and for at least 28 days after the last dose of etrasimod.
	Etrasimod is potentially teratogenic in humans with a low genotoxic potential.	Males with female partners of childbearing potential must agree to use contraception throughout the study period and for at least
	There is no margin of safety for these findings compared to therapeutic exposure range. Etrasimod should not be given to women who are pregnant, lactating, or breastfeeding.	28 days after the last dose of etrasimod.
Macular Edema.	Macular edema is an identified risk which requires specific ophthalmologic monitoring.	In this study, an ophthalmologic examination by an ophthalmologist is included at baseline (Screening) and for clinical monitoring of any signs or symptoms throughout the trial, as needed.

Potential Risk of Clinical Significance	Summary of Data/Rationale for Risk	Mitigation Strategy							
Study Procedures Blood Collection for PK									
Extravasation, bruising, local discomfort	Collection of 3 venous PK plasma samples each in Period 1 and 2.	Use of highly qualified nurses, with venipuncture experience.							
	Collection of 14 PK micro samples each in Periods 1 and 2.	Use of alternating arms for adjacent time points can provide more resting and healing time for each arm between samplings.							

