In both Periods 1 and 2, capillary blood samples (using micro sampling Tasso device) for PK analysis will be collected at predose and at 1, 2, 4, 6, 8, 12, 24, 48, 72, 96, 120, 144 and 168 hours postdose (SoA). Venous blood samples for PK analysis will be collected predose and at 2 and 4 hours postdose (SoA). Micro PK sampling occurs after venous PK blood sampling; samples will be taken from the alternate arms from one sampling time to the next.

Participants will be screened within 28 days of the first dose of study intervention and if all entry criteria are fulfilled, the participants will report to the CRU on the day prior to Day 1 dosing (Day -1). On Day 1 of each period, participants will receive a single dose of study intervention at the CRU. Administration of etrasimod will be oral via dosing of clinical IR

Treatment G: Single oral dose of etrasimod 2 mg, DCT without practice sessions** (Test)

^{*} Practice of Tasso and Wearable Monitoring Devices on Day 2 at CRU; participant self-assessment remotely for vitals and ECG (Days 3-5) and PK samples (Days 3-8)

^{**} Participant self-assessment using Tasso and Wearable Monitoring Devices on Days 1-2 at CRU; and remotely on Days 3-8

tablet 2 mg with water as per dosing instructions. Participants will be fasted for at least 10 hours predosing and 4 hours postdosing.

Participants will be confined in the CRU for a total of at least 2 days and discharged on Day 2 of each Period. A follow-up phone call will be made at least 28 calendar days and up to 35 calendar days after the last administration of the study intervention to capture any potential AEs and confirm appropriate contraceptive usage.

Tolerability and safety will be assessed for all treatments by monitoring AEs. Participants who withdraw from the study or whose PK samples are determined to be non-analyzable may be replaced at the discretion of the of the investigator upon consultation with the sponsor.

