4.2.1. Rationale for ECG Measurements

In the heart, $S1P_1$ is expressed on atrial myocytes and is associated with the regulation of heart rate. $S1P_1$ agonism activates both G alpha i (Gi) and β -arrestin signaling pathways. β -arrestin activation leads to receptor internalization, while Gi coupled signaling activates GIRK channels that regulate potassium efflux and membrane potential. As a result, there is a transient, first dose associated, chronotropic (slowing of HR) and dromotropic (slowing of AV nodal conduction) effects associated with etrasimod (a class effect). For all Phase 1 studies, intensive ECG have been taken for the first 6-hours post first dose. For this study, this practice should be in place until the NDA is approved.

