7.1.2. ECG Changes

Participants must permanently discontinue study intervention if suspected intolerance associated with first dose cardiac effects (Section 2.3.1).

If an ECG shows a new onset QTc interval above 500 ms during the treatment period, a repeat ECG is warranted. If this abnormal finding is confirmed, study intervention must be interrupted. Effective diagnostic and therapeutic strategies should be employed.

Reversible causes of prolonged QTc interval (eg, electrolyte abnormalities or hypomagnesemia), should be corrected as clinically indicated. When evaluating a participant with new onset QTc interval above 500 ms, referral to a cardiologist experienced in treating cardiac conduction disorders should be considered. Re-initiation of study treatment can only be considered after all of the following have occurred:

- The QTcF interval is <450 ms (males) or <470 ms (females),
- The QTc prolongation is considered by the investigator and confirmed by the cardiologist as not related to study treatment and likely caused by other factors,
- Individual risk-benefit is favorable (as determined by the investigator, in agreement with the cardiologist), and
- After discussion with the Medical Monitor.

If a clinically significant finding is identified (including, but not limited to, changes from baseline in QTcF after enrollment), the investigator or qualified designee will determine if the participant can continue in the study and if any change in participant management is needed. This review of the ECG printed at the time of collection or acquired using wearable monitoring device must be documented. Any new clinically relevant finding should be reported as an AE.

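### Sections 2.3.1 and 7.1.2 of the protocol give different triggers for permanent discontinuation after first-dose cardiac effects, and taken literally they disagree on whether the expected heart-rate fall bars the Period 2 dose.

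*Protocol*

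**What the plan says.** Two mandatory sentences in the protocol govern stopping after first-dose cardiac effects.

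- Section 2.3.1 (Risk Assessment), row on the first-dose cardiac effect, mitigation column: "Participants with cardiac effects associated with first dose will be required to permanently discontinue study intervention".
- Section 7.1.2 (ECG Changes), opening sentence: "Participants must permanently discontinue study intervention if suspected intolerance associated with first dose cardiac effects (Section 2.3.1", where the quote ends at the cross-reference.

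The protocol also says what the first-dose effect is. The rationale column of the same Section 2.3.1 row reads "S1P receptor modulators class of drugs is associated with an expected, on-target effect of reducing HR when first dosed". Section 2.2.4.2 reports that "etrasimod caused expected mild, transient, and generally asymptomatic reduction in HR at first dose" and describes the heart-rate effects as ones "which are transient and not clinically adverse or associated with safety findings". Section 4.2.1 adds slowed AV nodal conduction: "As a result, there is a transient, first dose associated, chronotropic (slowing of HR) and dromotropic (slowing of AV nodal conduction) effects associated with etrasimod".

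On the design, Section 4.1 states: "On Day 1 of each period, participants will receive a single dose of study intervention at the CRU". The cell that holds the stopping sentence also plans hourly heart-rate monitoring for the first 6 hours in all dose periods. SAP Section 6.2.2.1 summarizes the Day 1 heart-rate nadir for each period.

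**The concern.** Both sections prescribe permanent discontinuation, but for different events. Section 2.3.1 is triggered by the effect itself, and Section 7.1.2 by suspected intolerance associated with it. The protocol expects the effect in this population and calls it not clinically adverse, so the gap between the triggers is not confined to rare cases. It includes the ordinary response to the first dose.

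With a single dose per period, permanent discontinuation after Period 1 means that the Period 2 dose, Treatment G, is not given. Two things are at stake. One is consistent application of a safety rule in healthy participants: the same person could be dosed again or not, depending on which section the site follows. The other is the primary comparison of G with F, which has 8 planned participants and loses a pair with each stop.

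**Working it through.** The point rests on no stated figure, so the check sets the passages side by side.

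**Step 1. Compare the two rules.**

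| Element | Section 2.3.1 | Section 7.1.2 |
|---|---|---|
| Action | Permanent discontinuation | Permanent discontinuation |
| Trigger | Cardiac effects associated with the first dose | Suspected intolerance associated with those effects |
| Qualifier (rate, symptom, duration) | None | None; intolerance is undefined |
| Cross-reference | None for this rule | Back to Section 2.3.1 |
| Force | Mandatory | Mandatory |

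**Step 2. Ask whether the Section 2.3.1 trigger includes the expected effect.** The row is about the first-dose cardiac effect, and its rationale explains this as the expected on-target heart-rate reduction. Taken literally, the trigger therefore includes that reduction.

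**Step 3. Apply both rules to one participant.** Take someone whose only finding after the Period 1 dose is the expected asymptomatic fall. Under the literal Section 2.3.1 the participant must stop. Under Section 7.1.2 the participant need not stop, because an effect without suspected intolerance does not meet the trigger. The outcomes are opposite.

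**Step 4. Look for text that settles it.**

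- The cross-reference does not help, because Section 2.3.1 contains no definition of intolerance.
- Section 7.1 gives adverse event, pregnancy and withdrawal by the participant as reasons for stopping, in a list that is not stated to be complete.
- Appendix 7 lists ECG findings that may qualify as AEs or SAEs, but neither Section 2.3.1 nor Section 7.1.2 ties the stopping rule to it.

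**Step 5. Cost of one stop.** The planned sample is 8 (Section 9.5), so one withheld Period 2 dose removes 1/8 = 12.5% of the G profiles and of the G/F pairs, if the participant is not replaced.

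The effect on precision can be shown only conditionally. For an analysis of n complete pairs, the expected half-width of the 90% interval on the log scale is proportional to t(0.95, n−1)/√n. The within-participant SD is not given, but it cancels in the ratio to n = 8:

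- n = 8: 1.895/√8 = 0.670 (reference)
- n = 7: 1.943/√7 = 0.734, ratio 1.10
- n = 6: 2.015/√6 = 0.823, ratio 1.23
- n = 4: 2.353/√4 = 1.177, ratio 1.76

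These values of n are assumptions, not forecasts. The SAP's mixed model can also draw some information from an unpaired F profile, so the ratios are approximate for that model.

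**The case against.** The best defence is that the two passages are meant to be read together. Section 7.1.2 is the operative discontinuation section and cites Section 2.3.1 by number. The sentence in Section 2.3.1 is one line in a mitigation column, in a table of risks of clinical significance. An effect the protocol calls not clinically adverse is not, by itself, among the reasons listed in Section 7.1. Scheduled dosing in both periods, hourly monitoring in all dose periods and a nadir summary for each period all presume that participants with the expected fall go on to Period 2.

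Much of this stands. A coherent joint reading exists, and a site may well adopt it. That lowers the chance that doses are withheld for the expected effect. It does not remove the conflict: both sentences are mandatory, no text says which governs, and the term that would separate them is undefined.

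Three stronger readings are tempting but unsupported.

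- **A collision over QTc.** For a confirmed new QTc above 500 ms, Section 7.1.2 says "If this abnormal finding is confirmed, study intervention must be interrupted" and sets conditions for re-initiation. A reader might infer that this contradicts the permanent stop in Section 2.3.1. However, re-initiation requires that the prolongation be judged unrelated to study treatment, and such a case is not readily one associated with the first dose. The documents describe the first-dose effect as slowing of heart rate and AV conduction, not as QTc prolongation.
- **A count of lost doses.** A reader might infer that up to all 8 Period 2 doses would go under one rule and almost none under the other. The documents give no rate for either trigger.
- **Selective loss.** A reader might infer that the most heart-rate-sensitive participants would drop out of the G/F comparison. If any fall qualifies, the stop need not be selective. If only marked falls qualify, that is no longer the literal Section 2.3.1 rule. No document supports either pattern.

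Replacement also limits the loss. Sections 4.1 and 9.5 allow it, at the investigator's discretion after consulting the sponsor, for participants who withdraw from the study or whose data or PK samples are non-analyzable. Whether this covers someone who stops dosing but stays in the study is arguable, because Section 7.1 says that stopping treatment is not withdrawal.

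**Conclusion.** The inconsistency is real and concerns the trigger, not the action. For a participant with only the expected asymptomatic heart-rate fall, the literal Section 2.3.1 withholds the Period 2 dose and Section 7.1.2 does not. The literal Section 2.3.1 rule also sits badly with a design that doses and monitors heart rate in both periods.

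The size per event is known and the frequency is not. The 12.5% loss per stop assumes no replacement, and the number of stops cannot be quantified from the documents. First-dose heart-rate data from Period 1 are collected under either rule; a stop loses the Period 2 dose and the data that follow from it.

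The conclusion rests on reading the Section 2.3.1 sentence as written, alongside the rationale in its own row. It takes no view on which trigger is clinically right. The passages should be reconciled because a safety stopping rule should not depend on which section the site consults.

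**What to change.** Reconcile Sections 2.3.1 and 7.1.2 so that one trigger, in the same words, appears in both. If the term intolerance is kept, define it where the cross-reference points. State explicitly whether the expected asymptomatic heart-rate reduction meets the trigger. The threshold is a clinical decision for the sponsor.

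The cost is a wording amendment to two sections, with no new data, visits or participants.
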